6.1.1 Serious Adverse Events (SAEs)

An AE should be classified as an SAE and reported as such if it meets one or more of the

following criteria:

- Led to death
- Led to serious deterioration in the health of the subject, that either resulted in
 - Life threatening illness or injury,
 - Permanent impairment of a body structure or a body function, or
 - Inpatient or prolonged hospitalization, or
 - Medical or surgical intervention to prevent life-threatening illness or injury or permanent impairment to a body structure or a body function,
- Led to fetal distress, fetal death, or a congenital abnormality or birth defect
- Considered a significant medical event by the investigator based on medical judgment (e.g., may jeopardize the subject or may require medical/surgical intervention to prevent one of the outcomes listed above).

Hospitalizations for the following reasons will not be recorded as SAEs:

- Hospitalization or prolonged hospitalization for diagnostic or elective surgical procedures for preexisting conditions.
- Hospitalization or prolonged hospitalization required to allow outcome measurement for the study.
- Hospitalization or prolonged hospitalization for scheduled therapy of the target disease of the study.

6.1.2 Sight-Threatening Events

A sight-threatening event should be reported as an SAE. Sight-threatening events include, but are not limited to endophthalmitis, corneal decompensation, severe retinal detachment, severe choroidal hemorrhage, severe choroidal detachment, or aqueous misdirection.

6.1.3 Unanticipated Adverse Device Effects

An unanticipated adverse device effect (UADE) is any serious adverse effect on health or safety or any life-threatening problem or death caused by or associated with a device, if that effect, problem, or death was not previously identified in nature, severity or degree of incidence in the investigational plan or application (including a supplementary plan or application). UADEs also include any unanticipated sight-threatening events and any other unanticipated serious problem associated with a device that relates to the rights, safety, or welfare of subjects.

6.2 Adverse Event Assessment and Documentation

All subjects who undergo attempted implantation of the Hydrus will be evaluated for adverse events. All adverse events, regardless of severity and whether or not they are ascribed to the Hydrus implant or delivery system, will be recorded using standard medical terminology. All events for the study eye, fellow eye, and non-ocular are to be recorded.

All adverse events will be evaluated beginning with onset, and evaluation will continue until resolution is noted, or until the investigator determines that the subject's condition is stable.

The investigator will take appropriate and necessary therapeutic measures required for resolution of the adverse event. Any medication necessary for the treatment of an adverse event must be recorded.

All AEs will be characterized by the following criteria:

- Event term
- Severity
- Expectedness
- Relationship to study device or procedure
- Outcome
- Treatment or action taken.

Whenever possible, recognized medical terms should be used when recording AEs. Colloquialisms and/or abbreviations should not be used. Only one medical concept, preferably a diagnosis instead of individual symptoms, should be recorded as the event.

If more than one distinct adverse event occurs, each event should be recorded separately.

However, if known at the time of reporting, a diagnosis (i.e., disease or syndrome) should be recorded rather than individual signs and symptoms (e.g., record congestive heart failure rather than dyspnea, rales, and cyanosis). However, if a constellation of signs and/or symptoms cannot be medically characterized as a single diagnosis or syndrome at the time of reporting, each individual event should be recorded as a separate AE. A diagnosis that is subsequently established should be reported as follow-up information. However, signs and symptoms that are considered unrelated to an encountered syndrome or disease should be recorded as individual AEs (e.g., if congestive heart failure and severe headache are observed at the same time, each event should be recorded as an individual AE).

Events occurring secondary to other events should be recorded as sequelae to the primary cause; a "primary" event, if clearly identifiable, should represent the most accurate clinical term to record as the AE. Treatment for an adverse event should not be recorded as the adverse event. Instead, the reason for the treatment or procedure should be assessed as the potential adverse event.

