5.4 Safety Analyses

Adverse events (AEs) will be classified as intraoperative or postoperative. The AEs will be summarized by counts and percentages. They will also be summarized by severity (mild, moderate, severe) and relationship to the study device and implantation procedure.

Additionally, the frequency and percentage of the serious adverse events will be presented. The summaries of the adverse events will be separated by ocular and non-ocular events.

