6.8.1 Anticipated Adverse Events

Anticipated AEs associated with glaucoma surgical procedures that might reasonably be expected to occur in this study are listed below. These specific examples of anticipated AEs include, but are not limited to:

Intraoperative Adverse Events

- Choroidal hemorrhage or effusion
- Corneal abrasion
- Corneal edema
- Cyclodialysis cleft
- Hyphema obscuring the surgeon's view
- Inadvertent perforation of the sclera
- Iridodialysis
- Lens / capsular bag damage (crystalline or IOL)
- Microstent malposition
- Significant iris injury or trauma
- Vitreous loss
- Zonular dialysis

Postoperative adverse events include

- Angle closure
- Angle recession
- Anterior chamber cell or flare requiring either an increase in the standard postoperative steroid regimen or re-initiation of steroid use following completion of the standard postoperative steroid regimen.
- Aqueous misdirection
- Atrophy, phthisis
- Best-corrected visual acuity loss of 2 lines (10 letters) or more compared to baseline on the ETDRS chart measured before or at 1-month postoperative
- Best-corrected visual acuity loss of 2 lines (10 letters) or more compared to baseline on the ETDRS chart measured after 1-month postoperative
- Blebitis
- Choroidal detachment
- Choroidal hemorrhage or effusion (detachment with at least a partially hemorrhagic component that obstructs or causes pain, including both peripheral and "kissing" choroidal detachments) lasting 30 days or less
- Choroidal hemorrhage or effusion (detachment with at least a partially hemorrhagic component that obstructs or causes pain, including both peripheral and "kissing" choroidal detachments) lasting longer than 30 days
- Chronic anterior uveitis defined as inflammation of grade 1+ or worse persisting for more than 90 days postoperatively or that recurs less than 90 days after discontinuing standard medication regimen
- Chronic pain in the study eye onset ³ 3-months postoperative
- Corneal decompensation

- Corneal edema persisting > 30 days (mild to moderate) or severe corneal edema ≥ 1 day.
- Corneal opacification
- Descemet's membrane detachment
- Device migration (dislodgement or movement)
- Device obstruction
- Elevated mean IOP ≥ 10 mmHg than the qualifying baseline mean IOP onset before or at 1-month postoperative
- Elevated mean IOP ≥ 10 mmHg than the qualifying baseline mean IOP onset after 1-month postoperative
- Endophthalmitis

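### Sections 6.2 and 6.8.1 leave open whether a vision or pressure threshold event attributed to another adverse event is counted, so its reported rate may be too low

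*Combined protocol and SAP*

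**What the plan says.** Section 6.2 gives several recording rules:

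- On secondary events: "Events occurring secondary to other events should be recorded as sequelae to the primary cause". The primary event becomes the AE term on condition that it can be clearly identified.
- On the unit of recording: "Only one medical concept, preferably a diagnosis instead of individual symptoms, should be recorded as the event".
- On multiple events: "If more than one distinct adverse event occurs, each event should be recorded separately". The word distinct is not defined.
- Directly after that, introduced as a qualification: where it is known, "a diagnosis (i.e., disease or syndrome) should be recorded rather than individual signs and symptoms".

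Section 6.8.1 lists anticipated AEs, introduced by "These specific examples of anticipated AEs include, but are not limited to". Three items are defined by a measured threshold, and each has two entries divided at 1 month. One is IOP at least 10 mmHg above the qualifying baseline mean, one is IOP below 6 mmHg, and one is vision loss, of which the later entry reads "Best-corrected visual acuity loss of 2 lines (10 letters) or more compared to baseline on the ETDRS chart measured after 1-month postoperative". The same list includes possible causes as entries of their own, among them cyclodialysis cleft, hyphema, corneal edema, macular edema and device obstruction.

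Section 5.4 says of the analysis: "The AEs will be summarized by counts and percentages". It adds breakdowns by severity and by relationship to device and procedure, and a summary of serious events. It does not mention sequelae.

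**The concern.** A 10-letter loss or a pressure outside its limit can be both a listed event and the consequence of another listed event. Under the sequela rule it goes under its cause; under the Section 6.8.1 list it has its own entry. Two sites that both follow the document could record the same clinical course differently.

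The document describes no comparator arm, so the safety message rests on absolute event rates. A recording rule that lowers a rate has no control group to offset it, and differences between sites in naming a cause would pass straight into the tables.

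**Working it through.** The plan states no sample size, expected AE rate or other figure on this point, so there is nothing to reproduce. The check is textual, followed by a scale calculation on assumed values.

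**1. Can both rules apply to one subject?** Yes. Section 5.2 itself names a cyclodialysis cleft as an AE that lowers IOP, and Section 6.8.1 lists both the cleft and IOP below 6 mmHg. For a subject with both, the sequela rule gives one AE (the cleft) and the rule on distinct events gives two.

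**2. Does Section 6.2 say which rule wins?** No. The sentence on distinct events is followed by the preference for a diagnosis over its signs. Individual recording is then called for when signs and symptoms are judged unrelated to the diagnosed condition. A letter loss or pressure reading attributed to a diagnosis can fairly be read as a related sign and left out. Pointing the other way, Section 6.8.1 lists causes and consequences side by side (hypotony and hypotonic maculopathy, for instance). Its closing text also calls hypotony an adverse event even when incorrect device position may explain it. Neither reading is excluded.

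**3. Where does a sequela go?** Section 6.6 has an outcome category for resolution with sequelae, to be specified. That category describes how the primary AE ended, so a loss that later recovers need not appear there. Severity and relationship are assigned to each AE (Section 6.2) and tabulated by AE (Section 5.4). No text assigns them to a sequela.

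**4. Would another planned output show the events?** The schedule in Section 4.0 has ETDRS BCVA at baseline and seven postoperative visits (7 days to 12 months), and IOP at baseline and eight postoperative visits (1 day to 12 months).

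| Event | Own AE entry assured? | Other planned summary | Subject count at threshold |
|---|---|---|---|
| BCVA loss of 10 letters or more | No | None named in Section 5 | None |
| IOP below 6 mmHg | No | IOP by visit (5.3.3), with range (5.1) | None |
| IOP at least 10 mmHg above baseline | No | IOP change by visit (5.3.3), with range (5.1) | None |

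A visit minimum below 6 mmHg shows that at least one subject crossed the limit, but not how many did. Listings of individual data may be provided under Section 5.1, but they are optional.

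**5. Scale, on assumptions only.** Let f be the share of threshold events entered solely as a sequela of another AE and not tabulated. Then

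reported rate = true rate × (1 − f).

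With an assumed true BCVA-loss rate of 10%:

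- f = 0: 10% × 1 = 10%
- f = 0.25: 10% × 0.75 = 7.5%
- f = 0.50: 10% × 0.50 = 5%
- f = 0.75: 10% × 0.25 = 2.5%

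Two sites with the same true 10%, one at f = 0 and one at f = 0.50, would report 10% and 5%. Neither the 10% nor any value of f comes from the documents. The formula gives the direction of the bias and its range, not an estimate.

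**The case against.** The best defence is that Section 6.2 already requires distinct events to be recorded separately, and that Section 6.8.1, by naming these thresholds beside their possible causes, shows that they are distinct. On that reading f is 0 and nothing is lost. The reading is reasonable, but the document does not impose it.

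Other parts of the defence stand and limit the point:

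- The sequela rule is conditional: the cause must itself be an event, and a clearly identifiable one. A reader might infer that the rates shrink whenever any cause is found; the text does not support that.
- Some causes may fall below their own listed definitions. Postoperative hyphema is listed if layered to at least 2 mm or present or arising after 30 days; corneal edema if beyond 30 days, or severe for at least 1 day. There may then be no listed primary event to absorb the loss. This is only partial protection, because the list is not exhaustive and the AE definition in Section 6.1 is broad.
- Entry as a sequela is still entry. What is missing is a statement that it is counted.
- Permanent impairment and sight-threatening events are reported as serious (Sections 6.1.1 and 6.1.2), and Section 5.4 summarizes serious events. The gravest visual outcomes therefore have another route into the report.
- Section 6.8.1 gives examples of anticipated AEs. A reader might take these rates for the trial's main safety results, but Section 5.4 designates no safety endpoint.

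**Conclusion.** The conflict between the two sections is real and unresolved. The reported rates of the three threshold events may be too low and may vary with investigator attribution. BCVA loss is the most exposed, since no planned analysis outside the AE tables would show it. For IOP the loss is partial: extremes are visible by visit, subject counts are not.

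The documents do not determine the size. The undercount is zero if sites treat these events as distinct or if sequelae are tabulated, and it grows in proportion to f otherwise. It would be wrong to infer a certain undercount, because that assumes every attributed event is coded only as a sequela and then left out of the tables, and the plan says neither. The point is worth acting on because the data that remove the uncertainty are already scheduled for collection.

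**What to change.** **In Section 5.4**, add the number and percentage of Safety Population subjects with each of the following, derived by program from the scheduled visit data regardless of AE coding:

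- BCVA loss of 10 letters or more from baseline (ETDRS)
- IOP below 6 mmHg
- IOP at least 10 mmHg above baseline

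Split each at 1 month as its own entry in Section 6.8.1 does. The entries differ: the 1-month point belongs to the early period for BCVA loss and IOP elevation, and to the late period for hypotony.

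Two definitions are needed. First, state which visit IOP and which baseline IOP are used: Section 6.8.1 speaks of mean IOP against a qualifying baseline mean, while diurnal IOP is scheduled postoperatively only at 12 months. Second, show how many subjects have data in each period, because a note to the schedule has subjects who do not receive the microstent followed for 1 month, or until a device-related AE has resolved or is stable.

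**In Section 6.2**, state that an event meeting a numeric threshold in Section 6.8.1 is recorded as its own AE and linked to its cause.

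The cost is one sentence in Section 6.2, the definitions above and a few extra tables. Reported event rates may turn out higher. No new data are needed.

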6.3 Classification of Adverse Events by Severity

All adverse events should be graded on a three-point scale (mild, moderate, severe) for severity. The definitions are as follows:

Mild: Transient discomfort; no medical intervention/therapy required and does not interfere with daily activities.

Moderate: Low level of discomfort or concern with mild to moderate limitation in daily activities; some assistance may be needed; minimal or no medical intervention/therapy required.

Severe: Extreme discomfort and limitation in daily activities, significant assistance required; **significant** medical intervention/therapy required.

There is a distinction between the severity and the seriousness of an adverse event. Severity is a measurement of intensity; thus, a severe reaction is not necessarily a serious adverse event (SAE). For example, a headache may be severe in intensity, but would not be serious unless it met one of the criteria for serious adverse events listed in the protocol.

6.4 Anticipated or Unanticipated Events

All AEs will be evaluated as to whether they are anticipated or unanticipated.

Anticipated: An adverse event is anticipated (i.e., expected) when the nature, severity, or degree of incidence was previously described. Expected adverse events are listed in 8.8.1.

Unanticipated: An adverse event is unanticipated (i.e., unexpected) when the nature, severity, or degree of incidence was not previously described.

6.5 Relationship of the Event to the Device and Procedure

The study investigator will evaluate if the AE is related to the Hydrus device or the Hydrus procedure. Relationship is defined in the following manner:

Not related: Evidence indicates no plausible direct relationship to the study device or procedure, such that:

- A clinically plausible temporal sequence is inconsistent with the onset of the AE and device or procedure; and/or
- A causal relationship is considered biologically implausible; and/or
- The AE can be attributed to concurrent/underlying illness, other drugs, or procedures.

Related: Evidence indicates a reasonable temporal sequence of the event with the study device or procedure exists, or that the association of the event with study device administration is unknown and the event is not reasonably supported by other conditions, such that:

- There is a clinically plausible time sequence between onset of the AE and study device or procedure; and/or
- There is a biologically plausible mechanism for study device or procedure causing or contributing to the AE; and
- The AE cannot be reasonably attributed to concurrent/underlying illness, other drugs, or procedures.

Remote: Exposure to the device/procedure and the occurrence of adverse event cannot be reasonably determined to be unrelated to the device or the procedure.

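### The relationship categories in 6.5 overlap, so a possibly device-caused adverse event with a disease explanation can be coded Not related or Remote, depending on the rater

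*Combined protocol and SAP*

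**What the plan says.** Section 6.5 has the investigator place each adverse event in one of three categories.

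- *Not related* opens "Not related: Evidence indicates no plausible direct relationship to the study device or procedure, such that" and then gives three criteria: timing, mechanism and alternative cause. The connector is visible in the second, "A causal relationship is considered biologically implausible; and/or", and the third reads "The AE can be attributed to concurrent/underlying illness, other drugs, or procedures".
- *Related* asks for plausible timing and/or a plausible mechanism, and adds with a plain *and* that "The AE cannot be reasonably attributed to concurrent/underlying illness, other drugs, or procedures". Its opening sentence also admits events where "the association of the event with study device administration is unknown and the event is not reasonably supported by other conditions".
- *Remote* has a single sentence: "the occurrence of adverse event cannot be reasonably determined to be unrelated to the device or the procedure".

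Section 5.4 uses the result in the safety tables: "They will also be summarized by severity (mild, moderate, severe) and relationship to the study device and implantation procedure". It does not say whether *Remote* counts as device-related.

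**The concern.** An alternative explanation should rule out the device only if it leaves no role for the device. The third *Not related* criterion does not ask for that. It requires neither implausible timing nor an implausible mechanism, and it lacks the qualifier *reasonably* that appears in the matching *Related* criterion.

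The population makes this matter. Section 3.2 requires refractory glaucoma, either after a failed filtering or cilioablation procedure or with IOP uncontrolled on maximum tolerable medication. A disease explanation is therefore readily available for several events listed in 6.8.1, such as a mean IOP at least 10 mmHg above the qualifying baseline, or a confirmed loss of at least 3.0 dB in mean deviation. The same events could also reflect a stent that is not working. No control arm is described that would help separate disease from device, and 6.5 names only the investigator as judge. At stake is whether the 5.4 breakdown by relationship means the same thing from one rater to the next.

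**Working it through.** The documents give no sample size, expected event rate or device-related rate, so there is no plan figure to reproduce. The check is mainly logical.

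**Test case.** Take an event with plausible device timing, a plausible device mechanism and a reasonable disease explanation. Apply each definition in 6.5.

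1. *Related*: the timing and mechanism criteria are met. The alternative-cause criterion is not, and on the natural reading it is mandatory. The event is not *Related*, even though the mechanism criterion recognises a contributing role for the device.
2. *Not related*: the third criterion is met, and under the connector one criterion is enough. The opening sentence is not met, because a direct relationship is plausible. The definition conflicts with itself for this event.
3. *Remote*: met, because the event cannot reasonably be declared unrelated.

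Two categories remain open, with no order of precedence. If the *Related* criteria were grouped differently, so that plausible timing alone sufficed, the event would fit all three and the overlap would be wider.

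**Illustration 1: spread between raters (assumed counts).** Suppose 10 of 100 eyes have such an event and each disease explanation is judged reasonable. If *k* of the 10 are coded *Remote* and 10 − *k* *Not related*, these events contribute:

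- *Related*: 0/100 = 0%
- *Related* plus *Remote*: *k*/100, from 0% (*k* = 0) to 10% (*k* = 10)

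**Illustration 2: possible shortfall (assumed rates).** Let *p* be the true device-caused event rate and *q* the share of those events that could also be attributed to the disease. Ignoring misclassification in the other direction, the observed *Related* rate is *p* × (1 − *q*).

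| *p* | *q* = 10% | *q* = 30% | *q* = 50% |
|---|---|---|---|
| 10% | 9% | 7% | 5% |
| 30% | 27% | 21% | 15% |

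If all the disputed events are coded *Remote*, and *Remote* is pooled with *Related*, the combined rate returns to *p* and the shortfall is zero. If they are coded *Not related*, pooling recovers nothing. The documents give neither *p* nor *q*, nor a pooling rule, so the table shows how the rule behaves and does not estimate this study's bias.

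**The case against.** The strongest reply is that the opening sentence of *Not related* governs its criteria. An event with plausible timing and mechanism fails that sentence, so a careful rater would choose *Remote*. This is a fair reading, but not the only one. The criteria are presented as the ways in which the opening condition is shown, so a rater who relies on the third alone is also following the text.

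Second, recognised device failures have their own event terms in 6.8.1: obstruction, migration, malposition and implant-corneal touch. Section 6.2 prefers a diagnosis to individual signs and records secondary events as sequelae of the primary one. Section 6.8.1 also calls for gonioscopy, and ultrasound biomicroscopy if needed, when incorrect device position may be the cause. An IOP rise traced to a blocked inlet can therefore be recorded as obstruction and coded *Related*. This stands, and it limits the problem to events whose device cause has not been identified.

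Third, *Related* has provisions that work upward. Timing or mechanism alone is enough once alternatives are excluded, and an unknown association without a supporting condition also goes there. This stands too, and it is one reason why the net direction is not shown.

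Fourth, if 5.4 shows each category separately, a reader can add *Related* and *Remote*. That recovers events coded *Remote*, but not those coded *Not related*.

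**Conclusion.** The point holds as an ambiguity with a possible downward effect. The categories in 6.5 are not mutually exclusive for events with plausible device timing or mechanism plus a possible alternative cause. The 5.4 device/procedure-related rate can be understated and can vary with the rater. The size cannot be estimated from the documents.

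A reader might infer more, and three stronger readings are not supported:

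- *That the device-related rate is biased down.* This depends on how raters resolve the conflict and on whether *Remote* is pooled. Neither is stated.
- *That an IOP or field event in these eyes can never be Related.* The *Related* criterion turns on whether another cause is reasonable. That is a judgement on each event, and having refractory glaucoma does not settle it.
- *That the relationship summary is the study's only information on device harm.* Section 6.2 records all adverse events whether or not they are ascribed to the device. Section 5.4 reports all-cause and serious event counts, which do not depend on 6.5, and the device-specific terms speak to harm directly.

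The conclusion rests on the literal connector in *Not related* and on the natural grouping of the *Related* criteria. The effect is confined to the breakdown by relationship.

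**What to change.** In 6.5, make the categories mutually exclusive:

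- *Not related* should require an inconsistent time sequence, an implausible mechanism, or another cause that explains the event and excludes a contribution from the device or procedure. A possible alternative cause should no longer be enough alone.
- Events with plausible timing or mechanism plus a possible alternative cause should go to *Remote*. Renaming it, for example to *Possibly related*, is optional, but would avoid suggesting that a device role is unlikely.

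In 5.4, define the device/procedure-related rate as *Related* plus *Remote* combined, and show each level as well.

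The cost is a few lines of wording and one extra row in the adverse event table. The downside is a somewhat higher reported device-related rate, since the combined row will include some events that the disease caused. Showing each level lets the reader see how much of the rate comes from *Remote*.
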